2.2 Secondary Objective

The secondary objective is to assess for potential clinical benefits of participating in the MLHC program accompanied by the Epic Care Companion application. To assess this we will evaluate healthcare system utilization, COPD severity, health related quality of life, COPD medication use, smoking status, vaccination status, COPD knowledge, self-efficacy scores, self-management scores, and healthcare provider referrals prior to using the program vs. after program completion.

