4.2 Participant Recruitment and Screening

We will target a recruitment of 50 patients with physician diagnosed COPD. The patients will be recruited from the WCH Respirology Program clinics (as patients must be followed at WCH in order to use the Epic Care Companion app component). Recruitment will be accomplished through: advertisement posters in the Respirology clinic directing patients to discuss participation with their WCH Respirologist, and referrals from clinicians/circle of care. The potential participant's respirolgist will be the one to determine interest/consent in the participant being contacted for the study.

Participants who have expressed interest in the study will be contacted by study personnel (for example, a research assistant) to discuss potential participation in the study. Patients will not be compensated for their participation.

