4.7 Participant Withdrawal Criteria

4.7.1 When and How to Withdraw Participants

Participants are free to withdraw from participation in the clinical trial at any time. An investigator may discontinue or withdraw a participant from the clinical trial for the following reasons:

- Pregnancy;
- If any adverse event (AE), laboratory abnormality, or other medical condition or situation occurs such that continued participation in the clinical trial would not be in the best interest of the participant;
- Disease progression which requires discontinuation of the study intervention;
- If the participant meets an exclusion criterion (either newly developed or not previously recognized) that precludes further study participation

MLHC study

The reason for participant discontinuation or withdrawal from the study will be recorded within the participant's research record, and/or legal health record.

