4.7.2 Follow -up for Withdrawn Participants

If a participant withdraws consent, they can also request the withdrawal of their data and/or biological specimens subject to any research-specific restrictions, if applicable. Once withdrawn from the clinical trial, no further research procedures or evaluations will be performed, or additional research-specific data collected on the participant. Reasonable effort will be made to obtain permission to document the reason for withdrawal.

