6.0 RESEARCH PROCEDURES

6.1 Research Visits

- Pre-Screening Visit / Screening Visit (virtual or in-person)
 - Informed consent
 - Review of eligibility criteria
 - Orientation to the Epic Care Companion MLHC companion app
 - This visit will be performed by study staff (research assistant, or study investigators)
- Baseline Visit (virtual)
 - Collection of baseline outcome data
 - This visit will be performed by CREs as part of the MLHC program, study staff (research assistant, or study investigators) will confirm data collection and if needed supplement data collection using Epic or by contacting the participant

MLHC study

- Delivery of MLHC program 6 virtual sessions over 12 weeks, delivered by CREs, no outcome collection during this phase of the study
- Follow-up Visit at 3 months post baseline (virtual)
 - o Collection of follow-up outcome data
 - This visit will be performed by CREs as part of the MLHC program, study staff (research assistant, or study investigators) will confirm data collection and if needed supplement data collection using Epic or by contacting the participant
- Follow-Up Visit at 6 months post baseline (virtual)
 - o Collection of follow-up outcome data
 - This visit will be performed by CREs as part of the MLHC program, study staff (research assistant, or study investigators) will confirm data collection and if needed supplement data collection using Epic or by contacting the participant

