7.2 Sample Size Determination

As this is a pilot study, a sample size of 50 participants was chosen in order to adequately evaluate system feasibility first and foremost. The clinical outcomes of interest will be collected and analyzed, but the study will not be powered to capture a specific predicted difference at this stage. The results we do obtain will help inform the sample size calculations for a future larger clinical trial with control group.

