7.3 Populations for Analyses

Feasibility outcomes will be assessed for all patients referred to study enrolment Clinical outcomes will be assessed for all patients who complete the MLHC program and provide follow-up information. Essentially a Per-Protocol Analysis format.

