7.4.3 Analysis of the Secondary Endpoint(s)

Clinical endpoints:

Assessed prior to study start, at 3 months (end of MLHC program) and at 6 months (follow-up after program completion). Outcomes will be collected by MLHC CREs using a standardized form in Salesforce, as well as a research assistant based on Epic electronic chart review. For continuous variables, difference in the mean (SD) will be calculated at 3 months and 6 months compared to baseline. For dichotomous variables, difference in proportions at 3 and 6 months compared to baseline will be calculated.

MLHC study

- Healthcare system utilization (number of COPD-related outpatient visits, hospital admissions, ED visits, ICU admissions (at baseline will be over the previous 12 months)
- COPD severity (CAT and mMRC scores, and number of COPD exacerbations)
- Health related quality of life (CAT score)
- COPD medication use (COPD controller medication use, oxygen therapy, oral corticosteroid use, antibiotic use, rescue inhaler use)
- Smoking status (packs per year, quit attempts)
- Vaccination status (routine guidelines recommended vaccines received)
- COPD knowledge (Adapted COPD-Q score)
- Self-efficacy score (Adapted COPD Self-efficacy scale score)
- Self-management score (Partners in Health Scale score)
- Healthcare provider referrals prior to using the program (pulmonary rehab, smoking cessation counseling referrals

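### Section 7.3 confines the clinical outcomes to program completers, so starters who stop sessions but stay in the trial are left out even when they can be followed

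*Protocol*

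**What the plan says.** Section 7.3 of the protocol sets two populations. Feasibility outcomes use everyone referred. For the clinical endpoints: "Clinical outcomes will be assessed for all patients who complete the MLHC program and provide follow-up information". The section describes this as essentially per-protocol. Section 7.4.3, which describes the clinical analysis, names no wider set.

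Other sections bear on who could be followed:

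- Section 6.1 and the schedule in 6.2 time the two follow-up visits at 3 and 6 months from baseline, not from the last session attended. The educators conduct these visits within the program, but study staff may "if needed supplement data collection using Epic or by contacting the participant".
- Section 7.4.3 has outcomes collected by the educators "as well as a research assistant based on Epic electronic chart review".
- Section 4.2 recruits only from the hospital's own respirology clinics, because "patients must be followed at WCH in order to use the Epic Care Companion app component".
- Section 4.7.2 ends collection on withdrawal: "Once withdrawn from the clinical trial, no further research procedures or evaluations will be performed, or additional research-specific data collected on the participant". Section 4.7.4 treats unreachable participants as withdrawn. Section 4.7 does not address a participant who stops sessions but does not withdraw.

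On use of the results, section 7.2 says: "The results we do obtain will help inform the sample size calculations for a future larger clinical trial with control group".

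**The concern.** Completing the program is something that happens after baseline, and it may be related to how a participant fares. The protocol expects some non-completion, since completed over started is a primary endpoint. It also lists an outcome-related ground on which an investigator may withdraw someone: "Disease progression which requires discontinuation of the study intervention".

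In a single-arm study the before-after change is the only evidence on clinical benefit. There is no comparison group in which the same selection might partly cancel, so any selection into the analysis set goes straight into the estimate. The feasibility ratio will show how many starters did not complete, but not how they fared.

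At stake is whether the reported change describes people who took up the program or only those who finished it. Section 2.2 asks about benefit from participating, and section 7.2 intends the results to feed into later planning.

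**Working it through.** **Which exclusions section 7.3 itself causes**

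1. Participants who withdraw or are lost have no further research data under 4.7.2 and 4.7.4. They are missing under any analysis set.
2. Participants who stop sessions but do not withdraw still have visits due at 3 and 6 months from baseline, and 6.1 and 7.4.3 give routes to their data. Only the completion condition in 7.3 removes them.

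**Inputs.** The protocol gives 50 participants (7.2) but no completion rate, retention rate, standard deviation or expected change. There is therefore no figure of the plan's own to reproduce, and everything below except the 50 is assumed. Assume all 50 start, and let

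- a = number analysed under 7.3 (completed and followed up), with mean change m;
- s = number who stopped sessions and can be followed;
- D = mean change in the session-stoppers minus m.

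**Formula.** The mean over a + s participants is [a·m + s·(m + D)]/(a + s) = m + s/(a+s) × D. The shift caused by the 7.3 rule is therefore s/(a+s) × D. The largest possible s is 50 − a.

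**Shift in CAT points**

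| a | s | s/(a+s) | D = 0 | D = +2 | D = +4 |
|---|---|---|---|---|---|
| 45 | 2 | 0.043 | 0 | 0.09 | 0.17 |
| 45 | 5 (limit) | 0.100 | 0 | 0.20 | 0.40 |
| 35 | 0 | 0 | 0 | 0 | 0 |
| 35 | 5 | 0.125 | 0 | 0.25 | 0.50 |
| 35 | 10 | 0.222 | 0 | 0.44 | 0.89 |
| 35 | 15 (limit) | 0.300 | 0 | 0.60 | 1.20 |
| 30 | 10 | 0.250 | 0 | 0.50 | 1.00 |
| 30 | 20 (limit) | 0.400 | 0 | 0.80 | 1.60 |

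A negative D gives the same sizes with the sign reversed. Take a rise in CAT as worsening (an assumption, consistent with 7.4.4 treating increased severity as a concern). A positive D then means that completers look better than all followed starters, and a negative D that they look worse.

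**Example.** With a = 35, s = 10 and an assumed m of −2, the estimate over all followed starters is −2.44, −2.00, −1.56 or −1.11 for D = −2, 0, +2 or +4.

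**What 7.3 does not cause.** If withdrawn and lost participants shared the same D, the full gap between the analysed and all 50 starters would be (50 − a)/50 × D. At a = 35 and D = +4 this is 0.300 × 4 = 1.20. After subtracting the shift above, 1.20, 0.70, 0.31 and 0 remain for s = 0, 5, 10 and 15. Changing 7.3 cannot recover that remainder.

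**Scale.** In units of the standard deviation of change, the standard error of a mean over 45 people is 1/√45 = 0.149. With a = 35, s = 10 and D = 0.5 SD, the shift is 0.222 × 0.5 = 0.11 SD, somewhat less than one standard error. At the limit s = 15 with D = 1 SD it is 0.30 SD, against 1/√50 = 0.141.

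**The case against.** The case for leaving 7.3 alone has real force.

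- **The choice is disclosed and low in rank.** The set is labelled per-protocol, the endpoints are secondary, section 7.1 tests no hypothesis and section 7.2 claims no power. This stands and limits the weight of the point. But a label does not supply the outcomes left out.
- **The objective may fit completers.** Section 2.2 compares outcomes "prior to using the program vs. after program completion". A reader might infer that 7.3 contradicts the objective. It does not: the phrase can be read as timing or as describing people who finished. Neither reading requires a completers-only set, and no section promises an all-starters estimate.
- **The affected group may be small or empty.** Section 4.7 does not describe people who stop sessions and stay. The protocol also does not say how many of the six sessions count as completing, so a lenient reading would exclude few. This stands; with s = 0 the effect is zero.
- **Questionnaires are harder to obtain than chart data.** The educators do the follow-up visits within the program. Staff may contact participants, so CAT, knowledge and self-efficacy scores are possible but not assured. Utilization and medication data can come from Epic. This also stands.
- **Planning use is loose.** A reader might turn the shift into extra participants per arm for the later trial. The documents do not support that: an uncontrolled within-person change is not a between-arm difference in either analysis set.

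**Conclusion.** The point holds in a limited form. Section 7.3 fixes a completers-only set by a stated rule, and that rule discards starters who stop sessions but can still be followed. The before-after change can then differ from that among all followed starters by s/(a+s) × D. In the assumed scenarios this runs from 0 to 1.60 CAT points in size, with 0.44 to 0.89 in the middle case (a = 35, s = 10, D = 2 to 4). These figures rest wholly on assumed values of a, s and D and on all 50 participants starting.

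Three stronger readings are not supported:

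- **That the plan overstates benefit.** Nothing in the protocol fixes the sign of D. There is no shift if session-stoppers change equally, and benefit is understated if they do better.
- **That 7.3 accounts for every missing participant.** Losses after withdrawal or loss of contact come from 4.7.2 and 4.7.4.
- **That the safety review covers completers only.** Section 7.4.4 names no population, and adverse event recording, the early termination visit and escalation by educators are not tied to completion.

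The change is worth making, but the study's primary feasibility purpose is unaffected.

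**What to change.** In section 7.3, define the main clinical set as all participants who started MLHC and have baseline data, regardless of sessions attended. Use all available 3- and 6-month data, including utilization, medication and exacerbation data from Epic. Keep the completer analysis as supportive. Report how many starters lack follow-up at each time point, and why.

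For consistency, state in 4.7 and 6.1 that stopping sessions is not in itself withdrawal from the trial, so the 3- and 6-month assessments still apply to those who continue to consent. This concerns data collection only, not when anyone should stop sessions. No change to 4.7.2 or 7.4.4 is needed for this point.

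The cost is a few sentences of protocol text, a little more analysis and some extra contacts by existing staff, which 6.1 already allows. The estimates may be less favourable, and more questionnaire data will be missing in the wider set. The completer result is still reported, so nothing now planned is lost.

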7.4 Statistical Analyses

7.4.1 General Approach

7.4.2 Analysis of the Primary Endpoint(s)

Feasibility endpoints:

- MLHC program participation
 - Number of patients who started program over total offered
 - Number of patients who completed program over total started
 - o Number of providers who referred patients to the program over total
- MLCH Care Companion app use
 - o Number of times app opened
 - Number of sessions accessed within the app
 - Number of session tasks marked completed
 - Use of other app features (ex: medication reminder notifications)
 - Time spent using the app each time used

7.4.3 Analysis of the Secondary Endpoint(s)

Clinical endpoints:

Assessed prior to study start, at 3 months (end of MLHC program) and at 6 months (follow-up after program completion). Outcomes will be collected by MLHC CREs using a standardized form in Salesforce, as well as a research assistant based on Epic electronic chart review. For continuous variables, difference in the mean (SD) will be calculated at 3 months and 6 months compared to baseline. For dichotomous variables, difference in proportions at 3 and 6 months compared to baseline will be calculated.

MLHC study

- Healthcare system utilization (number of COPD-related outpatient visits, hospital admissions, ED visits, ICU admissions (at baseline will be over the previous 12 months)
- COPD severity (CAT and mMRC scores, and number of COPD exacerbations)
- Health related quality of life (CAT score)
- COPD medication use (COPD controller medication use, oxygen therapy, oral corticosteroid use, antibiotic use, rescue inhaler use)
- Smoking status (packs per year, quit attempts)
- Vaccination status (routine guidelines recommended vaccines received)
- COPD knowledge (Adapted COPD-Q score)
- Self-efficacy score (Adapted COPD Self-efficacy scale score)
- Self-management score (Partners in Health Scale score)
- Healthcare provider referrals prior to using the program (pulmonary rehab, smoking cessation counseling referrals

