7.0 STATISTICAL CONSIDERATIONS

7.1 Statistical Hypotheses

This is a pilot study of feasibility, so there are no a priori null hypotheses to test

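### Event counts fall under the difference-in-means rule with a 12-month baseline set against 3- and 6-month follow-up, so an unchanged event rate would look like a fall

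*Protocol*

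**What the plan says.** Section 7.4.3 states the clinical analysis in two sentences: "For continuous variables, difference in the mean (SD) will be calculated at 3 months and 6 months compared to baseline" and "For dichotomous variables, difference in proportions at 3 and 6 months compared to baseline will be calculated". The same rules appear in section 3.3 and in the Clinical Trial Summary. Section 7.4.1 (General Approach) has no text, so these two rules are all that the protocol specifies for clinical outcomes.

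The outcomes under these rules include numbers of COPD-related outpatient visits, hospital admissions, ED visits and ICU admissions, and the number of COPD exacerbations. For utilization, all three places add that the baseline figure covers the 12 months before. No window is given for the counts at 3 and 6 months, and none at any visit for exacerbations. Sections 6.1 and 6.2 place the follow-up visits 3 and 6 months after baseline.

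The stated aims are modest: "This is a pilot study of feasibility, so there are no a priori null hypotheses to test" (7.1), and "the study will not be powered to capture a specific predicted difference at this stage" (7.2). Section 7.2 adds: "The results we do obtain will help inform the sample size calculations for a future larger clinical trial with control group".

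**The concern.** A count has meaning only with the time over which it was collected. The protocol fixes a 12-month window at baseline, gives follow-up times of 3 and 6 months, and then asks for a difference between the two. That difference mixes any change in event rate with the change in window length, and the window always pushes it downwards.

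Two uses are at stake. Under section 2.2 the utilization outcomes are evidence of potential clinical benefit, and a spurious fall would favour the program. Under sections 7.4.4 and 8.5 the same outcomes are examined at 3 and 6 months for a rise, with study termination among the steps that may be considered, and a spurious fall would hide a rise. In addition, a mean with an SD describes sparse, skewed counts poorly.

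**Working it through.** **Inputs from the protocol.** Baseline window 12 months (3.3, 7.4.3). Follow-up 3 and 6 months after baseline (6.1, 6.2). Planned sample 50 (7.2), with clinical outcomes restricted to completers who give follow-up data (7.3), so 50 is an upper limit. The protocol gives no event rates.

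**Step 1: expected raw counts when nothing changes.** Let the rate be λ events per person-year throughout, and let follow-up counts run from baseline.
- Baseline mean count: λ × 12/12 = λ.
- 3 months: λ × 3/12 = 0.25λ. Difference −0.75λ, a 75% fall.
- 6 months: λ × 6/12 = 0.50λ. Difference −0.50λ, a 50% fall.
- If the 6-month visit counts only events since the 3-month visit, the window is again 3 months and the fall is 75%.

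The percentages do not depend on λ. For illustration, with assumed rates:

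| Assumed λ | Baseline mean | 3 months (difference) | 6 months (difference) |
|---|---|---|---|
| 0.2 | 0.20 | 0.05 (−0.15) | 0.10 (−0.10) |
| 1.0 | 1.00 | 0.25 (−0.75) | 0.50 (−0.50) |
| 2.0 | 2.00 | 0.50 (−1.50) | 1.00 (−1.00) |

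**Step 2: how large a rise would be hidden.** The raw difference is zero when follow-up rate × window equals λ × 12 months. That needs a rate 12/3 = 4 times baseline at 3 months and 12/6 = 2 times baseline at 6 months.

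**Step 3: does the proportions rule escape this?** If counts were reduced to any event versus none, the Poisson probability of at least one event is 1 − exp(−λT), with T in years. At λ = 1 (assumed) this is 0.632 over 12 months, 0.221 over 3 and 0.393 over 6. The differences are −0.411 and −0.239 with no change in rate. The window problem remains.

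**Step 4: the alternative reading of the window.** Suppose follow-up also looked back 12 months. The windows would then match, but 9 of the 12 months at the 3-month visit, and 6 of 12 at the 6-month visit, would precede the program. For a true rate ratio R, the observed ratio is 0.75 + 0.25R at 3 months and 0.50 + 0.50R at 6 months. A true halving (R = 0.5) would appear as 0.875 and 0.75. This reading dilutes change instead of inventing it.

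**Step 5: sparseness.** Under a Poisson model the share of participants with no event in 3 months is exp(−λ/4): 95% at λ = 0.2 and 78% at λ = 1 (both assumed). A mean (SD) says little about such data.

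**Step 6: what a rate would give.** With all 50 analysed, person-years are 50 at baseline, 50 × 0.25 = 12.5 at 3 months and 50 × 0.5 = 25 at 6 months. The approximate 95% half-width is 1.96 × √(λ/person-years). At λ = 1 it is ±0.28, ±0.55 and ±0.39. The rates are then on one scale, and the intervals show how little the short windows can say.

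**Step 7: the minor clarification.** The text does not say whether the SD is that of change or that at each visit. With equal visit SDs and within-person correlation r, their ratio is √(2(1 − r)): 1.18, 1.00, 0.77 and 0.45 at r = 0.3, 0.5, 0.7 and 0.9 (assumed). The two should not be confused, so one phrase of definition is worthwhile.

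**The case against.** The strongest reply is that this is a descriptive feasibility pilot, that "a sample size of 50 participants was chosen in order to adequately evaluate system feasibility first and foremost", and that count models, intervals and the exact SD belong in a statistical analysis plan that is not shown. This holds for intervals, for which SD is meant and for paired summaries of proportions; their absence from the protocol is no fault. It does not cover the windows. The protocol itself fixes the 12-month baseline, the follow-up times and the form of the comparison, and these do not fit together.

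It can also be said that the protocol never calls admissions or ED visits continuous. That is true, but only two rules are offered and step 3 shows that neither works. Section 7.4.4 does speak of exacerbation rates, so investigators may well use rates when looking at safety; section 7.4.3 does not carry that through. Case-by-case discussion under section 8.5 is unaffected.

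A reader might infer more: that the planned summaries lack any SD of change and so cannot inform the size of a later trial. The documents do not support this. An SD is named and can be read as the SD of change, and section 7.2 promises only to help inform. Either SD can size a two-arm trial. For an assumed effect of 0.3 SD (two-sided 5%, 80% power), the visit SD alone gives 2 × (1.96 + 0.84)²/0.3², about 175 per arm. That is conservative against the 159 to 34 per arm with baseline adjustment at r = 0.3 to 0.9. Marginal proportions of 0.4 and 0.6 (assumed) give 97 per arm. The individual data allow paired quantities to be computed at any time.

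Nor does the plan propose treating repeated visits as independent samples, so no inflation of the SD of change can be charged to it.

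**Conclusion.** The point holds for event counts. Followed as written, with follow-up counts running from baseline, section 7.4.3 would show a 75% fall at 3 months and a 50% fall at 6 months in mean utilization with no change in rate. It would also mask a rise of up to fourfold or twofold respectively. These figures rest only on the window lengths and a constant underlying rate; the illustrative rates and the Poisson model affect only the examples. If follow-up was meant to look back 12 months, the artefact becomes dilution, and the text still needs to say so. Exacerbations have no stated window and carry the same risk.

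Rates remove the window artefact only. Participants enter because of at least one exacerbation in the previous 12 months (4.4.1) and there is no control group, so some fall in rate could still occur without any program effect.

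The definition of the SD and a paired interval are clarifications; no stated result is wrong without them.

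**What to change.** In section 7.4.3, and in the matching text of section 3.3 and the Clinical Trial Summary:

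- Report outpatient visits, ED visits, hospital admissions and ICU admissions as rates per person-year with 95% confidence intervals, for the 12 months before baseline and for each follow-up window. Compare the rates in place of mean (SD) counts.
- State each follow-up window, including whether the 6-month count starts at baseline or at the 3-month visit.
- State the look-back window for exacerbations and treat them in the same way.
- As a clarification, say that the SD for continuous scores is that of within-participant change, and give a paired 95% confidence interval.

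A mixed model using all available visits is not needed for this. It would have to be reconciled with section 7.3, under which "Clinical outcomes will be assessed for all patients who complete the MLHC program and provide follow-up information".

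The cost is a few lines of text, and a check that the collection form and chart review use the stated windows. No new visits or measurements are required.
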